# **Resources:**

The PI will oversee the study through weekly meetings to ensure proper study protocol adherence and recruitment and data progress. A study coordinator in the Pulmonary Division will conduct day to day activities of the study such as mailing of participant documents, data collection and input, and time points to send out materials. All mailing and data input will occur on Gonda 18 in the research laboratory.

## Subject Information

Target accrual: 60 patients

Subject population: Patients on the heart and lung transplant waiting lists

Inclusion Criteria: Aged 18 or older, consenting to research, and listed (active and temporarily inactive) or deferred for lung or heart transplantation at Mayo Clinic in Rochester, MN

Exclusion Criteria: Patients will be excluded if ineligible for transplant, non-English speaking, non-verbal or extremely hard of hearing.

## **Research Activity**

Check all that apply and complete the appropriate sections as instructed.

1. Drug & Device: Drugs for which an investigational new drug application is not required. Device for which (i) an investigational device exemption application is not required; or the medical device is cleared/approved for marketing and being used in accordance with its cleared/approved labeling. (Specify in the Methods section)

- 2. Blood: Collection of blood samples by finger stick, heel stick, ear stick, or venipuncture.
- 3. Biological specimens other than blood: Prospective collection of human biological specimens by noninvasive means that may include: urine, sweat, saliva, buccal scraping, oral/anal/vaginal swab, sputum, hair and nail clippings, etc.
- 4. Tests & Procedures: Collection of data through noninvasive tests and procedures routinely employed in clinical practice that may include: MRI, surface EEG, echo, ultrasound, moderate exercise, muscular strength & flexibility testing, biometrics, cognition testing, eye exam, etc. (Specify in the Methods section)
- 5. 🖾 **Data** (medical record, images, or specimens): Research involving use of existing and/or prospectively collected data.
- 6. Digital Record: Collection of electronic data from voice, video, digital, or image recording. (Specify in the Methods section)
- 7. Survey, Interview, Focus Group: Research on individual or group characteristics or behavior, survey, interview, oral history, focus group, program evaluation, etc. (Specify in the Methods section)

NIH has issued a *Certificate of Confidentiality* (COC). *When checked, provide the institution and investigator named on the COC and explain why one was requested.* 

# **Review of medical records, images, specimens** – Category 5

**For review of existing data**: provide a date range or an end date for when the data was generated. The end date can be the date this application was submitted to the IRB. Example: 01/01/1999 to 12/31/2015 or all records through *mm/dd/yyyy*.

## Date Range:

Check all that apply (data includes medical records, images, specimens).

(5a) Only data that exists before the IRB submission date will be collected.

 $\boxtimes$  (5b) The study involves data that exist at the time of IRB submission **and** data that will be generated after IRB submission. Include this activity in the Methods section. Examples

- The study plans to conduct a retrospective chart review and ask subjects to complete a questionnaire.
- The study plans to include subjects previously diagnosed with a specific disease and add newly diagnosed subjects in the future.

(5c) The study will use data that have been collected under another IRB protocol. Include in the Methods section and enter the IRB number from which the research material will be obtained. *When appropriate, note when subjects have provided consent for future use of their data and/or specimens as described in this protocol.* 

Enter one IRB number per line, add more lines as needed

🗌 Data	Specimens Data & Specimens	
🗌 Data	Specimens Data & Specimens	
🗌 Data	Specimens Data & Specimens	

(5d) This study will obtain data generated from other sources. Examples may include receiving data from participating sites or an external collaborator, accessing an external database or registry, etc. Explain the source and how the data will be used in the Methods section.

 $\bigotimes$  (6) Video audio recording: All health coaching intervention sessions will be audio recorded. All recordings will be kept private, and all recordings will be destroyed at the end of the study.

### HIPAA Identifiers and Protected Health Information (PHI)

# Review the list of subject identifiers below and, if applicable, check the box next to each HIPAA identifier being recorded at the time of data collection or abstraction.

**Internal** refers to the subject's identifier that will be recorded at Mayo Clinic by the study staff. **External** refers to the subject's identifier that will be shared outside of Mayo Clinic.

Check all that apply:	INTERNAL	EXTERNAL
Name	Х	
Mayo Clinic medical record or patient registration number, lab accession,	Х	
specimen or radiologic image number		
Subject ID, subject code or any other person-specific unique identifying	Х	
number, characteristic or code that can link the subject to their medical data		
Dates: All elements of dates [month, day, and year] directly related to an	Х	
individual, their birth date, date of death, date of diagnosis, etc.		
Note: Recording a year only is not a unique identifier.		
Social Security number	Х	
Medical device identifiers and serial numbers		
Biometric identifiers, including finger and voice prints, full face photographic	Х	
images and any comparable images		
Web Universal Resource Locators (URLs), Internet Protocol (IP) address		
numbers, email address		
Street address, city, county, precinct, zip code, and their equivalent geocodes	Х	
Phone or fax numbers	Х	
Account, member, certificate or professional license numbers, health		
beneficiary numbers		
Vehicle identifiers and serial numbers, including license plate numbers		
Check 'None' when none of the identifiers listed above will be recorded,	None	Nona
maintained, or shared during the conduct of this study. (exempt category 4)		None None

#### Data Analysis

Power analyses and study endpoints are not required for minimal risk research, pilot or feasibility studies.

No statistical information. *If checked, please explain*: This is a pilot study to obtain preliminary data for future NIH grant application.

Power Statement: Not required for a pilot study.

Data Analysis Plan: Descriptive statistics and change in secondary endpoints.

Endpoints

Primary: Acceptability and feasibility of health coaching by thoracic transplant candidates. This will be obtained by looking at completion rate of intervention and qualitative surveys after the intervention is completed.

Secondary: Preliminary efficacy data for power calculation for larger R01 application and multisite study. We will look at change in patient reported outcomes of resilience, quality of life, affect, and self-management ability. We will also look at change in frailty parameters.

Health Coaching to Improve Self-Management in Thoracic Transplant Candidates NCT03150095 5/09/2017

PI: [name] MD, Mayo Clinic Rochester, MN

ANALYSIS PLAN: Sample size: This is a pilot and feasibility study. However, to inform our enrollment we have made the following calculations. Change in SMAS-30. A sample size of 25 in each group will have 80% power to detect an effect size of 0.81 using a two-group t-test with a 0.05 two-sided significance level, where effect size is the end of study difference in means between the two groups relative to the SD of the end of study measures, after adjusting for baseline and other factors. From the literature, we estimate an unadjusted end of study SD for SMAS-30 of 8.5. Whereas we do expect our intervention to impact SMAS-30, it is our clinical impression that without intervention, patients tend to exhibit similar patterns over time. Therefore, we expect the between-person variability in SMAS-30 to be at least as large as the variability in assessing SMAS-30 for the same person at different time points. If these two sources of variability were the same then they would both have a SD of 6.0, in particular the end of study SD for SMAS-30 would be 6.0 or less. With this SD, we would have power to detect a difference of 0.81x6.0=4.9. Thus, this pilot study is reasonably powered. Allowing for a 20% withdrawal rate (primarily due to transplantation during intervention), we will aim for a sample size of 30 per arm. Analysis plan: Demographic characteristics will be summarized by mean, median, SD and range (continuous variables) and counts and percents (categorical variables). Our primary variable will be end of study SMAS-30 (adjusting for baseline), which we will analyze using analysis of covariance (ANCOVA), estimating between group differences. Subgroup analysis will be performed by sex, ethnicity, and race as feasible. A similar procedure to that described above will be employed to impute data if necessary. Missing data and end of study SDs for SMAS-30, adjusting for baseline, will guide analysis and power calculations for future R01 studies. Secondary Outcomes will examine between group differences of changes in gait speed, activity levels, body composition, weights, and RISC-10, PANAS, MUIS, FDI, SMAO, and KCCO or CRO measures to inform future R01 planning. A two-tailed p< 0.05 will be considered statistically significant.

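### The SAP's upper limit of 6.0 for the baseline-adjusted SMAS-30 SD does not follow from its own assumption, which gives about 7.4, so 80% power for 4.9 points is not assured

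*SAP*

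**What the plan says.** The SAP's Sample size paragraph bases its power statement on a two-group t-test with 25 per arm, two-sided 0.05, 80% power and an effect size of 0.81. It defines the effect size as the end-of-study difference in means "relative to the SD of the end of study measures, after adjusting for baseline and other factors". The planned analysis matches that definition: "Our primary variable will be end of study SMAS-30 (adjusting for baseline), which we will analyze using analysis of covariance (ANCOVA").

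The conversion to points runs as follows.

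- Starting value: "From the literature, we estimate an unadjusted end of study SD for SMAS-30 of 8.5".
- Assumption: "we expect the between-person variability in SMAS-30 to be at least as large as the variability in assessing SMAS-30 for the same person" on separate occasions.
- Limiting case: "If these two sources of variability were the same then they would both have a SD of 6.0".
- Conclusion: "in particular the end of study SD for SMAS-30 would be 6.0 or less".
- Result: "we would have power to detect a difference of 0.81x6.0=4.9".

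From this the SAP judges the pilot to be adequately powered. It gives no correlation between baseline and end-of-study scores and does not name the other factors in the adjustment.

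**The concern.** The effect size is defined on the adjusted SD, so the SD that converts 0.81 into points must be the one left after adjustment. The SAP uses 6.0, which is one of the two components of the unadjusted 8.5, namely "the variability in assessing SMAS-30 for the same person at different time points". That component would equal the adjusted SD only if each person's long-run level were known exactly. ANCOVA conditions on one observed baseline score, which varies within the person just as the final score does, so part of the between-person variance stays in the residual.

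If so, 6.0 is not the upper limit that the SAP takes it to be, and the 4.9-point figure and the verdict on power both depend on a correlation that is not stated. A reader could judge a null pilot result against 80% power that the trial may not have had. If the same step were repeated when planning the larger study with equal components, the required sample size would come out about one third too small (1 − 36/54.19 = 0.336).

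**Working it through.** **Inputs, all from the SAP's Sample size and Analysis plan text:** 25 per arm; two-sided 0.05; effect size 0.81; unadjusted end-of-study SD 8.5; between-person variance at least equal to within-person variance; ANCOVA adjusting for baseline.

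**1. The SAP's separate figures reproduce.**
- t-test power at effect size 0.81, 25 per arm (noncentral t, 48 df): 80.1%. The effect size for exactly 80% is 0.809.
- Equal components: 8.5/√2 = 6.01 each.
- 0.81 × 6.0 = 4.86, given as 4.9.

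**2. The step from component to adjusted SD.** Write each score as a person's level (variance B) plus an occasion-specific deviation (variance W), with the same variances at both visits and independent deviations.
- Total variance: B + W = 8.5² = 72.25.
- Correlation of baseline with end of study: ρ = B/(B + W).
- Baseline-adjusted SD: 8.5 × √(1 − ρ²).

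With B = W = 36.125, ρ = 0.5, the adjusted variance is 72.25 × 0.75 = 54.19 and the adjusted SD is 7.36. The 54.19 consists of the within-person 36.125 plus 18.06 of between-person variance that one baseline score does not remove. The SAP's figure leaves out the 18.06.

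Since B ≥ W means ρ ≥ 0.5, the limit that follows from the SAP's assumption is about 7.4.

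**3. Consequence for power, 25 per arm.** The ANCOVA figures use a noncentral t with 47 df. The variance of the group effect is s² × (2/25) × (1 + T²/48), averaged over T from a t distribution with 48 df to allow for chance baseline imbalance. The t-test value is in brackets.

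| Correlation | Adjusted SD | Power for 4.9 points | Difference with 80% power |
|---|---|---|---|
| 0.5 | 7.36 | 62.6% (63.5%) | 6.02 (5.95) |
| 0.6 | 6.80 | 69.5% (70.4%) | 5.56 (5.50) |
| 0.7 | 6.07 | 79.0% (79.9%) | 4.96 (4.91) |
| 0.8 | 5.10 | 90.8% (91.4%) | 4.17 (4.12) |

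The last column is the effect size for 80% power (0.818 for ANCOVA, 0.809 for the t-test) times the adjusted SD. For example, 0.818 × 7.361 = 6.02.

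A simulation of 40,000 trials with two equal components and ANCOVA on one baseline score gave a residual SD of 7.36, power of 62.9% for 4.9 points (Monte Carlo standard error 0.24 percentage points) and 80.2% for 6.02 points (0.20).

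**4. What 6.0 would require.**
- From baseline alone: ρ = √(1 − (6.0/8.5)²) = 0.708. Between-person variance is then 0.708/0.292, or about 2.4 times within-person variance.
- From other covariates at ρ = 0.5: they must explain 1 − 36/54.19 = 0.336 of the remaining variance.

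**5. Dependence on the 8.5.** The literature source is not shown. As an illustration at ρ = 0.5, an unadjusted SD of 7.0 gives 79.1% ANCOVA power for 4.9 points, and 10.0 gives 49.2%.

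**The case against.** The strongest reply is that the SAP writes no explicit variance model. One could read its split as the part of the end-of-study variance explained by the earlier score and the part left unexplained. Equal parts would then make the left-over SD 6.0, and a larger explained part would make it smaller, so the sentence would be valid. This reading amounts to assuming a squared correlation of at least 0.5. It does not fit the SAP's words, which name variability between persons and variability of the same person over time. Those are components of the score itself, and they imply a correlation, not a squared correlation, of at least 0.5.

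A second reply is that the effect size also allows for other factors, which could bring the SD down to 6.0. They could, but the SAP names none and derives 6.0 from the variance split alone.

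Three points on the other side stand.

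- The 63% applies only at the edge of the assumption. The SAP expects patients to be fairly stable over time, and at a correlation of 0.7 power is already about 79%.
- Going from the component assumption to a correlation of at least 0.5 requires equal variances at the two visits and independent within-person deviations. A statement that gives the end-of-study SD and the correlation directly does not need those conditions.
- The practical weight is small. The protocol's Data Analysis section requires no power statement and makes acceptability and feasibility primary, and the SAP intends to estimate the adjusted SD from the trial for later planning.

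**Conclusion.** The concern holds, as a minor point. The t-test calculation is right; the error is in taking the within-person component as the upper limit of the baseline-adjusted SD. On the SAP's own assumption the limit is about 7.4, so 80% power for 4.9 points is possible but not assured. It is about 63% in the least favourable case, where the difference detectable with 80% power is about 6.0 points instead of 4.9. The SAP's figure is recovered if the baseline correlation, or the multiple correlation with other covariates, is about 0.71. These results rest on the literature SD of 8.5, on 25 evaluable patients per arm, and on the two-component reading with equal variances at both visits. Enrolment, endpoints and the planned analysis are unaffected.

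**What to change.** In the SAP's Sample size paragraph, replace the statement of the 6.0 limit and the 4.9-point sentence with wording such as:

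> Assuming an unadjusted SD of 8.5 and a baseline to end-of-study correlation of at least 0.5, the baseline-adjusted SD is at most about 7.4, and 25 evaluable patients per arm give 80% power for a difference of about 6.0 points in the least favourable case. Power for 4.9 points is about 63% in that case and reaches about 80% if the baseline correlation (or the multiple correlation with other covariates) is about 0.71.

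The cost is this change of wording and a less favourable stated detectable difference. It needs no additional patients and no change to the analysis.

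### The 20% withdrawal allowance is applied as 25 × 1.2 = 30 per arm, which leaves 24 evaluable rather than 25; power at effect size 0.81 is about 78%, a minor correction

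*SAP*

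**What the plan says.** The sample size paragraph of the SAP (ANALYSIS PLAN) starts from the evaluable number: "A sample size of 25 in each group will have 80% power to detect an effect size of 0.81". The test behind that figure is a t-test comparing the two arms at the two-sided 5% level. The paragraph turns the effect size into SMAS-30 points with an adjusted SD of 6.0: "With this SD, we would have power to detect a difference of 0.81x6.0=4.9". It then moves from evaluable to enrolled patients: "Allowing for a 20% withdrawal rate (primarily due to transplantation during intervention), we will aim for a sample size of 30 per arm". The protocol's Subject Information section has the matching total, "Target accrual: 60 patients".

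The status of the calculation also matters. The SAP introduces it with "This is a pilot and feasibility study. However, to inform our enrollment we have made the following calculations". The protocol's Data Analysis section says "Power Statement: Not required for a pilot study".

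**The concern.** An allowance for withdrawal is meant to leave the required number of patients after losses. The SAP does not say in words that 25 per arm will remain, but the step from 25 to 30 has no other evident purpose. At the SAP's own 20% rate, 30 does not leave 25. The 80% power and the 4.9-point detectable difference therefore belong to a slightly larger evaluable sample than the plan expects to have.

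Two things are at stake, both modest. The first is whether the SAP's planning figures agree with one another. The second is carry-over. Both documents say that the pilot will inform power calculations for a larger study. Multiplying by 1.2 to cover 20% loss leaves 1.2 × 0.8 = 0.96 of the evaluable sample required, which is 4% short at any trial size.

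**Working it through.** **Inputs, all from the SAP's sample size paragraph:** 25 evaluable per group; effect size d = 0.81; two-group t-test, two-sided 0.05; adjusted SD 6.0; withdrawal 20%; 30 enrolled per arm. The protocol's accrual of 60 agrees with 2 × 30.

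**Step 1. Reproduce the plan's power figure.** For n per group, the noncentrality is d × √(n/2) on 2n − 2 degrees of freedom.
- n = 25: 0.81 × √12.5 = 2.86 on 48 df, giving power of 80.1%.
- Solving for n at 80% power gives 24.92, so 25.
- Detectable difference: 0.81 × 6.0 = 4.86, which rounds to the stated 4.9.

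The statement for 25 per group is correct.

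**Step 2. Reproduce the enrolment figure.**
- n × (1 + w) = 25 × 1.2 = 30, the SAP's number.
- n / (1 − w) = 25/0.8 = 31.25, so 32 per arm, or 64 in total.
- Evaluable from 30: 30 × 0.8 = 24.
- Largest withdrawal rate at which 30 keeps 25: 1 − 25/30 = 16.7%.

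Only the first formula gives 30, and it does not preserve 25 at 20% loss.

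**Step 3. The effect of having 24 per arm.** The noncentrality is 0.81 × √12 = 2.81 on 46 df.

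| Evaluable per arm | Power at d = 0.81 | d detectable with 80% power | Points at SD 6.0 |
|---|---|---|---|
| 25 | 80.1% | 0.809 | 4.85 |
| 24 | 78.4% | 0.826 | 4.96 |

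The loss is 80.1 − 78.4 = 1.7 percentage points of power. The detectable difference rises by 4.96 − 4.85 = 0.11 SMAS-30 points.

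**Step 4. Sensitivity to method.** Giving up one degree of freedom for the baseline covariate in the planned ANCOVA leaves the results at 80.1% and 78.4%. A normal approximation gives 81.7% and 80.1%. However, the SAP names a t-test, and its 25 is the t-test answer; the normal approximation would have required only 24.

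**The case against.** The strongest reply is that the slip changes nothing that matters, and much of that stands.

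- **The power sentence is not false.** It is attached to 25 per group and reproduces there. A reader might infer from the withdrawal slip that the 80% claim is wrong, or that the SAP's description of the pilot as reasonably powered collapses. The documents do not support that: the claim holds for its own n, and 78% against 80% does not overturn a general description of that kind.
- **The inputs are softer than the gap.** The 20% is a round planning value. The SD of 6.0 comes from a literature figure reduced on clinical impression, and the SAP itself says it may be lower. With an SD of 5.9, the difference detectable with 24 per arm would be 0.826 × 5.9 = 4.87, which cancels the discrepancy.
- **It is a pilot.** The protocol requires no power statement and makes acceptability and feasibility primary. No decision in the plan turns on 78% against 80% power for SMAS-30.
- **Withdrawal need not mean exclusion.** The SAP allows imputation if necessary, although imputation does not fully restore the lost information.

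These points limit the size of the issue. They do not make 30 the right allowance for 20% loss from a target of 25. The SAP chose to calculate an enrolment number, and that number should follow from its own inputs.

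A reader might also be tempted to fold in the question of whether 6.0 is the right adjusted SD. That is a separate matter and should not be counted here. At any SD, the withdrawal step raises the detectable difference only by a factor of 0.826/0.809 = 1.02.

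**Conclusion.** The arithmetic error is certain and follows from the SAP's own figures: the enrolment target was obtained as 25 × 1.2, and 20% withdrawal from 30 leaves 24 per arm. Its size is small. Power at 0.81 is about 78% instead of 80%, and the effect detectable with 80% power is 0.83 (about 5.0 points) instead of 0.81 (4.9 points).

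This rests on three conditions: that the allowance was meant to leave 25 evaluable per arm, that withdrawal is exactly 20% in each arm, and that withdrawn patients contribute no outcome information. The point values also take the SAP's SD of 6.0 as given. It is a minor correction to a planning statement and does not show a materially underpowered pilot.

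**What to change.** Keep enrolment at 60 and amend one sentence in the SAP's sample size paragraph. Suggested wording: 30 patients per arm will be enrolled; after 20% withdrawal about 24 per arm are expected to be evaluable, which gives 80% power for an effect size of 0.83 (about 5.0 SMAS-30 points at an SD of 6.0) and about 78% power for an effect size of 0.81.

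If the sponsor prefers to leave 0.81 and 4.9 points in place, the SAP should say that they hold only if withdrawal is at most 16.7%. Raising enrolment to 32 per arm would also restore consistency, at a cost of 64 − 60 = 4 patients, but the size of the effect does not call for it. Planning for the larger study should use n/(1 − w).

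The cost is one line of text and a slightly less favourable stated detectable difference. No patients, procedures or analyses change.

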## Study Measures:

Participants will complete the following testing, SPPB measures, and wear an Actigraph at baseline and after completing the intervention (or in an equivalent time-frame if a control patient).

1. Hand grip strength test: Hand grip strength will be measured using a Jamar Digital Hand Held Dynamometer. Participants will complete the grip strength test 3 times with their dominant hand. The 3 trials will be averaged and adjusted by sex and BMI using a normative table.

2. Gait speed test: The participant's gait speed will be measured using a stopwatch as the participant walks a distance of 15 feet at a self-selected walking speed. The average of 3 trials will be calculated and adjusted for sex and height. To determine the participant's SPPB score, the results of the gait speed test will be prorated for 4 meters (13.1 feet). The best of 3 trials will be used to calculate the participant's SPPB score.

3. Short physical performance battery (SPPB): The SPPB consists of a gait speed test over 4 meters (13.1 feet), timed repeated chair stands, and 3 balance tests.

a. Gait speed test: See #2.

b. Timed repeated chair stands: Participants will be asked if they feel safe to stand from a chair without the use of their arms and without assistance. If the participant feels safe to stand from a chair without the use of their arms and without assistance, they will be asked to complete 5 repeated chair stands. The participant's SPPB score will be determined by the time required to complete 5 repeated chair stands.

c. Balance testing: The participant's balance will be tested in side-by-side, semi-tandem, and tandem stands. In the side-by-side stand, participants will stand with their feet as close together as possible. In the semi-tandem stands, participants will stand with one heel touching the big toe of the opposite foot. In the tandem stands, participants will stand with the heel of one foot in front of the toes of the other foot (as if on a balance beam). Participants will be asked to hold each position for up to 10 seconds.

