4. Body composition scan: Participants will stand on the InBody 770 body composition analyzer, which determines body composition by electrical impedance (i.e., sending an electrical signal through the body). Height, weight, BMI, skeletal muscle mass, percent body fat, and segmental lean mass will be recorded. Participants with a pacemaker, an implantable cardioverter-defibrillator (ICD), or an automated ICD (AICD) will not be able to complete this body composition scan. Those patients will have their height and weight collected. BMI will be calculated.

5. Activity monitoring: Participants will receive an Actigraph activity monitor to be worn on the wrist for 5-7 days. The activity monitors are capable of measuring the number of steps taken, the number of calories

burned, the intensity of physical activity, the amount of sedentary time, and other variables. Participants will receive a prepaid addressed envelope to return the activity monitor.

6. Center for Epidemiologic Studies Depression Scale (CES-D): Participants will answer 2 questions from the CES-D about their level of exhaustion.

7. Self-reported weight loss: Patients will be asked whether they intentionally lost 10 or more pounds within the last year. As available, weight changes in kg will also be abstracted from the medical record to trend the weight over the prior year's time.

8. Demographic information: Patients will be asked to self-report their sex, race, ethnicity, marital status, education level, and the relationship of their primary caregiver post-transplant.

9. Questionnaires:
Chronic Respiratory Questionnaire (lung disease only)
Kansas City Cardiomyopathy Questionnaire (heart disease only)
Mishel Uncertainty of Illness Questionnaire
Positive Affect Negative Affect Questionnaire (affect)
Perceived Stress Scale (stress)
PHQ 2 and GAD 2 (mood/affect)
RISC-10 (resilience)
Frailty Deficit Index (frailty)
SMAQ (adherence)
SMAS-30 (self-management)

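### The SAP names a baseline-adjusted model only for SMAS-30; the secondary outcomes are left as comparisons of change, and each outcome's baseline should be stated as a covariate

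*SAP*

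**What the plan says.** The SAP specifies the SMAS-30 analysis in full: "Our primary variable will be end of study SMAS-30 (adjusting for baseline), which we will analyze using analysis of covariance (ANCOVA"). It also says what SMAS-30 will contribute to the next trial: "Missing data and end of study SDs for SMAS-30, adjusting for baseline, will guide analysis and power calculations for future R01 studies".

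The remaining outcomes share one sentence: "Secondary Outcomes will examine between group differences of changes in gait speed, activity levels, body composition, weights", followed by RISC-10, PANAS, MUIS, FDI, the adherence measure and the heart- or lung-specific quality-of-life measure. No test, model or covariate is named. The SAP then sets a two-tailed 0.05 significance threshold.

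The Protocol's Data Analysis section does not fill the gap. It plans descriptive statistics and change for the secondary endpoints and states "We will look at change in patient reported outcomes of resilience, quality of life, affect, and self-management ability". It presents these endpoints as preliminary efficacy data for powering a larger R01 study.

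The baselines will be available. Under Study Measures: "Participants will complete the following testing, SPPB measures, and wear an Actigraph at baseline and after completing the intervention".

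**The concern.** The natural reading of the secondary sentence is that each patient's change is computed and mean changes are compared between arms. That fixes the slope on baseline at 1. ANCOVA estimates the slope, so it is more precise unless the best slope is already close to 1.

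The change score is not biased under randomisation; its only cost is extra variance. There are two consequences:

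- In this trial, intervals for the secondary outcomes may be wider than the collected data allow, in a small study that still applies a 0.05 threshold.
- For the next trial, the SD carried forward may be the SD of change, whereas the SAP plans to carry forward a baseline-adjusted SD for SMAS-30. The two differ, and a study sized on the first but analysed by ANCOVA would be too large.

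Two analysts could also follow the sentence faithfully and report different estimates and p-values.

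**Working it through.** **The plan's own figure.** The only power statement concerns SMAS-30: 25 per group, effect size 0.81, two-sided 0.05, 80% power. The noncentral t with 48 df gives 80.1%, and 0.81 × 6.0 = 4.86, which matches the stated 4.9. No such figure exists for any secondary outcome.

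**Inputs**

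- n = 25 per arm (SAP, sample size).
- r, the baseline to end-of-study correlation: not given for any secondary outcome, so it is an assumption shown as a range.
- The only anchor for r is the SAP's SMAS-30 illustration. Between- and within-person SDs of 6.0 each give a total variance of 36 + 36 = 72 and an SD of √72 = 8.49 (the SAP's 8.5). Then r = 36/72 = 0.5. Because "we expect the between-person variability in SMAS-30 to be at least as large as the variability in assessing SMAS-30 for the same person", the SAP implies r of 0.5 or more, but for a different outcome.
- n = 12 per arm for smaller subsets: an assumption. It stands for the organ-specific questionnaires and for body composition, since "Participants with a pacemaker, an implantable cardioverter-defibrillator (ICD), or an automated ICD (AICD) will not be able to complete this body composition scan".

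**Formulas** (equal baseline and end-of-study SD s)

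- Var(change) = 2(1 − r)s² × 2/n
- Var(ANCOVA) = (1 − r²)s² × 2/n × [1 + 1/(2n − 4)], where the bracket is the cost of estimating the slope: 1 + 1/46 = 1.0217 at n = 25 and 1 + 1/20 = 1.05 at n = 12
- Variance ratio, change/ANCOVA = [2/(1 + r)] / [1 + 1/(2n − 4)]

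At r = 0.5 and n = 25 the ratio is (2/1.5)/1.0217 = 1.333/1.0217 = 1.30.

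| r | Ratio, n = 25 | 95% CI half-width in SDs, n = 25: change v ANCOVA | Per-arm n for change to match ANCOVA with 25 | Ratio, n = 12 |
|---|---|---|---|---|
| 0.5 | 1.30 | 0.57 v 0.50 | about 33 | 1.27 |
| 0.7 | 1.15 | 0.44 v 0.41 | about 29 | 1.12 |
| 0.9 | 1.03 | 0.25 v 0.25 | about 26 | 1.00 |

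Half-widths use t with 2n − 2 df for change and 2n − 3 df for ANCOVA. Below the anchor, at r = 0.3, the ratio with 25 per arm is 1.51.

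**Break-even.** Setting the ratio to 1 gives r = 2/1.0217 − 1 = 0.957 at n = 25 and r = 2/1.05 − 1 = 0.905 at n = 12. Above these values ANCOVA is slightly worse (ratio 0.99 at r = 0.98, n = 25).

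**Unequal SDs.** With k = end-of-study SD / baseline SD, the ratio is (1 + k² − 2rk) / [k²(1 − r²)] / 1.0217 at n = 25. At r = 0.5:

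- k = 0.8: (0.84/0.48)/1.0217 = 1.71
- k = 1.25: (1.3125/1.1719)/1.0217 = 1.10
- k = 1.5: (1.75/1.6875)/1.0217 = 1.01 to 1.02

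**Simulation check.** With 40,000 null trials per setting, the ratios were 1.30, 1.15 and 1.03 (n = 25) and 1.27, 1.12 and 1.01 (n = 12) at r = 0.5, 0.7 and 0.9. Both estimators averaged within 0.003 SD of zero, so neither is biased.

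**Carry-forward to a larger trial.** There the slope cost is negligible and the size ratio is 2/(1 + r): 1.33, 1.18 and 1.05 at r = 0.5, 0.7 and 0.9. Sizing on the change-score SD and then analysing by ANCOVA would therefore enrol 33%, 18% or 5% more patients than needed.

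**The case against.** The strongest reply is that no wrong analysis is stated. The documents never say the comparison will be unadjusted, and their use of *change* is loose. The SAP's sample-size text is labelled as change in SMAS-30, yet defines the effect "relative to the SD of the end of study measures, after adjusting for baseline and other factors". The Protocol likewise lists self-management under change. A sponsor could say baseline adjustment was always meant. This stands as far as it goes: the defect is an unstated model, not a declared unadjusted one. If adjustment was intended, the edit only confirms it.

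A second objection is that the magnitude is not anchored. No r is documented for any affected outcome, and the one anchor belongs to the outcome that already has ANCOVA. Over the scenarios worked, the effect runs from a material gain to a slight loss. This also stands, and it is why the result is given as a range.

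Third, the SAP's explicit input for future power calculations is the adjusted SMAS-30 SD, so oversizing on a secondary outcome may never occur. This stands only in part. The Protocol assigns the secondary endpoints to power calculation for the larger study, so their SDs are planning inputs, though neither document says which SD would be used.

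Finally, this is a pilot, and the Protocol notes that power analyses and endpoints are not required. That limits the severity. But the SAP chose to name a model for SMAS-30 and a significance threshold, and the secondary sentence falls short of that standard.

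**Conclusion.** The concern holds at low severity. The SAP gives a baseline-adjusted model for SMAS-30 alone and leaves the other outcomes as comparisons of change with no model. If that is carried out without the covariate, the variance with 25 per arm and equal SDs is about 30% higher than necessary at r = 0.5, 15% at 0.7 and 3% at 0.9. There is nothing to gain at r of about 0.96, or about 0.90 with 12 per arm. These figures rest on assumed correlations and on 25 evaluable patients per arm; the results also shift with the ratio of end-of-study to baseline SD. Validity is not in question, and the loss can be recovered because the adjusted analysis can be run later on the same data. Naming the model in advance avoids choosing it after the results are seen.

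**What to change.** Replace the secondary-outcomes sentence in the SAP with wording such as:

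> Each continuous secondary outcome will be analysed by ANCOVA of the end-of-study value (or, equivalently, the change) on treatment arm, with its own baseline value as covariate. Adjusted differences between arms will be reported with 95% CIs, together with the baseline-adjusted SD, the correlation between baseline and end-of-study values, and the number of patients with both measurements. KCCQ and CRQ will be analysed within their organ group.

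Regressing the change or the end value on arm and baseline gives the same treatment estimate, so the language of change can stay, and mean changes can still be tabulated. The Protocol's endpoint text needs no rewording.

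The cost is one sentence, with no new data or visits. Each model loses one degree of freedom. For very stable measures there is a small precision loss: with equal SDs, at most about 2% in variance at 25 per arm and 5% at 12 per arm, these being the limits 1.0217 and 1.05 as r approaches 1.
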